8.2.1. Serious Adverse Events

An SAE is any AE from this study that results in 1 of the following outcomes:

- death
- initial or prolonged inpatient hospitalization
- a life-threatening experience (that is, immediate risk of dying)
- persistent or significant disability/incapacity
- congenital anomaly/birth defect
- important medical events that may not be immediately life-threatening or result in death or hospitalization but may jeopardize the patient or may require intervention to prevent one of the other outcomes listed in the definition above.

If an SAE occurs after signing the ICF, but prior to receiving investigational product, it needs to be reported ONLY if it is considered reasonably possibly related to study procedure.

Study site personnel must alert Lilly or its designee of any SAE within 24 hours of investigator awareness of the event via a sponsor-approved method. If alerts are issued via telephone, they are to be immediately followed with official notification on study-specific SAE forms. This

24-hour notification requirement refers to the initial SAE information and all follow-up SAE information.

Pregnancy (during maternal or paternal exposure to investigational product) does not meet the definition of an AE. However, to fulfill regulatory requirements any pregnancy should be reported following the SAE process to collect data on the outcome for both mother and fetus.

Investigators are not obligated to actively seek AEs or SAEs in subjects once they have discontinued and/or completed the study (the patient summary eCRF has been completed). However, if the investigator learns of any SAE, including a death, at any time after a subject has been discharged from the study, and he/she considers the event reasonably possibly related to the study treatment or study participation, the investigator must promptly notify Lilly.

8.2.2. Adverse Events of Special Interest

The following adverse events of special interest (AESIs) will be used to determine the safety and tolerability of ixekizumab over the range of doses selected for this clinical study.

AESIs for ixekizumab are:

- cytopenias (leukopenia, neutropenia, and thrombocytopenia)
- liver function test changes/enzyme elevations (ALT, AST, bilirubin, and alkaline phosphatase)
- infections
- injection-site reactions
- allergic reactions/hypersensitivities
- cerebrocardiovascular events
- malignancies
- inflammatory bowel disease (IBD)
- depression

Sites will provide details on AEs as instructed on the eCRF. Investigators will also educate patients and/or caregivers about the symptoms of systemic allergic/hypersensitivity reactions and will provide instructions on the management and reporting of these reactions. Blood samples will be collected as soon as possible for any patient who experiences an AE of a potential systemic allergic/hypersensitivity reaction during the study as judged by the investigator. These samples may be tested for ADAs, other laboratory tests needed to elucidate the cause of the allergic/hypersensitivity reaction, and/or ixekizumab serum concentration.

Data on preferred terms associated with cerebrocardiovascular events (defined as death, cardiac ischemic event including MI and hospitalization for unstable angina, hospitalization for heart failure, serious arrhythmia, resuscitated sudden death, cardiogenic shock, coronary revascularization procedure, stroke/transient ischemic attack, peripheral revascularization procedure, peripheral arterial event, and hospitalization for hypertension) will be collected, and

these events and any deaths will be adjudicated by an external Clinical Events Committee (CEC) made up of a chairperson, 2 cardiologists, and a neurologist.

Data on suspected IBD, as identified by events possibly indicative of ulcerative colitis and Crohn's disease, will be collected and the events will be adjudicated by an external CEC with expertise in IBD.

The role of the external CECs is to adjudicate defined clinical events in a blinded, consistent, and unbiased manner throughout the course of a study. The purpose of the CEC for adjudication of cerebrovascular events and the CEC for adjudication of suspected IBD events is to ensure that all reported events are evaluated uniformly by a single group.

8.2.2.1. Suspected Unexpected Serious Adverse Reactions

Lilly has procedures that will be followed for the recording and expedited reporting of SUSARs that are consistent with global regulations and the associated detailed guidances.

8.2.3. Complaint Handling

Lilly collects product complaints on investigational products and drug delivery systems used in clinical studies in order to ensure the safety of study participants, monitor quality, and to facilitate process and product improvements.

Patients will be instructed to contact the investigator as soon as possible if he or she has a complaint or problem with the investigational product so that the situation can be assessed.

8.3. Treatment of Overdose

Refer to the IB.

8.4. Safety Assessments

8.4.1. Electrocardiograms

For each patient, a 12-lead digital ECG will be collected locally at screening according to the Schedule of Activities ([Appendix 2](#)). Patients must be supine for approximately 5 to 10 minutes before ECG collection and remain supine but awake during ECG collection.

Electrocardiograms will be interpreted locally by a qualified physician as soon after the time of ECG collection as possible, and ideally while the patient is still present, to determine whether the patient meets entry criteria and for immediate patient management, should any clinically relevant findings be identified. The qualified physician must document his/her review of the ECG at the time of evaluation. Any clinically significant findings from ECGs that result in a diagnosis and that occur after the patient receives the first dose of the investigational treatment should be reported to Lilly or its designee as an AE via eCRF.

The ECGs will be maintained at the site and made available to the sponsor as requested.

8.4.2. Vital Signs

Vital signs (BP and pulse) and body temperature will be measured (sitting) after resting for a minimum of 10 minutes at visits indicated in the Schedule of Activities ([Appendix 2](#)). At baseline (Week 0) and Visit 7 (Week 12), BP and pulse should be measured prior to administration of the investigational product and again approximately 1 hour post-administration.

Any clinically significant findings from vital signs measurement that result in a diagnosis and that occur after the patient receives the first dose of study treatment should be reported to Lilly or its designee as an AE via eCRF. Additional measurements of vital signs may be performed at the discretion of the investigator.

8.4.3. Laboratory Tests

For each patient, laboratory tests detailed in ([Appendix 3](#)) should be conducted according to the Schedule of Activities ([Appendix 2](#)).

Any clinically significant findings from laboratory tests that result in a diagnosis and that occur after the patient receives the first dose of investigational product should be reported to Lilly or its designee as an AE via eCRF.

8.4.4. Physical Examination

For each patient, one complete physical examination (excluding pelvic, rectal, and breast examinations) will be performed at screening. This examination will determine whether the patient meets the criteria required to participate in the study and will also serve as a monitor for preexisting conditions and as a baseline for treatment-emergent adverse event (TEAE) assessment. All physical examinations throughout the study are indicated in the Schedule of Activities ([Appendix 2](#)) and should include a symptom-directed physical evaluation, as well as an examination of the heart, lungs, and abdomen and a visual examination of the skin.

Any clinically significant findings from a complete physical examination that result in a diagnosis and that occur after the patient receives the first dose of study treatment should be reported to Lilly or its designee as an AE via eCRF.

8.4.5. Chest X-Ray and Tuberculosis Testing

A posterior-anterior view chest x-ray will be obtained, unless the x-ray or results from a chest x-ray obtained within 6 months prior to the study are available. The chest x-ray or results will be reviewed by the investigator or designee to exclude patients with active TB infection.

In addition, patients will be tested at screening as indicated on the Schedule of Activities ([Appendix 2](#)) for evidence of active or latent TB indicated by a positive tuberculin PPD skin test response (≥ 5 mm induration, between approximately 2 and 3 days after test application, regardless of BCG vaccination history). In countries where an Interferon-Gamma Release Assay (QuantiFERON®-TB Gold test, and/or T-SPOT®) is available and in the judgment of the investigator preferred as an alternative to the PPD skin test for the evaluation of TB infection, it

may be used instead of the PPD test (positive tests excluded) and may be read locally. If the QuantiFERON®-TB Gold test is indeterminate, or the T-SPOT® is invalid or borderline, 1 retest is allowed. If the retest for the QuantiFERON®-TB Gold test is indeterminate, or the retest for the T-SPOT® is invalid or borderline, then the patient is excluded from enrollment in the study.

Patients with documentation of a negative test result within 3 months prior to baseline (Week 0; Visit 2) do not need a TB screen at Visit 1. Documentation of this test result must include a record of the size of the induration response (<5 mm induration). A PPD test recorded as negative without documenting the size of induration will result in a retest.

However, patients with a PPD skin test ≥ 5 mm induration or a positive QuantiFERON®-TB Gold or positive T-SPOT® test at screening, and patients who have documentation of a history of a positive TB test but do not have documentation of a history of at least 4 weeks of appropriate latent TB treatment, but no other evidence of active TB, may be rescreened 1 time and may be enrolled without repeating a PPD or QuantiFERON®-TB Gold test or T-SPOT® if the following conditions are met:

- after receiving at least 4 weeks of appropriate latent TB infection (LTBI) therapy prior to rescreening, with commitment by the patient and the investigator for the patient to complete a full course of prophylaxis for TB
- with no evidence of hepatotoxicity (ALT/AST must remain ≤ 2 times ULN) upon retesting of serum ALT/AST prior to randomization. Such patients must complete appropriate LTBI therapy during the course of the study in order to remain eligible
- meet all other inclusion/exclusion criteria for participation

If rescreening occurs within 6 months of the screening chest x-ray, there is no necessity for repeat of chest x-ray for considering enrollment.

Patients with positive TB test results on file: Patients with prior history of a positive TB test should not have a TB test performed at Visit 1. Documentation of this history and of at least 4 weeks of appropriate latent TB treatment prior to baseline (Week 0, Visit 2) is required for study eligibility. Patients who have a documented history of completing an appropriate TB treatment regimen with no history of re-exposure to TB since their treatment was completed and no evidence of active TB are eligible to participate in the study. Patients who have had household contact with a person with active TB are excluded, unless an appropriate and documented course of prophylaxis for TB was completed.

Any clinically significant findings from chest x-rays and/or tuberculosis testings that result in a diagnosis and that occur after the patient receives the first dose of study treatment should be reported to Lilly or its designee as an AE via eCRF.

8.4.6. Immunogenicity

Samples for immunogenicity testing, including samples that may be analyzed for ixekizumab concentration, will be collected at time points indicated in the Schedule of Activities

(Appendix 2). Additionally, blood samples for potential immunogenicity testing will be collected, as soon as possible, for any patient who experiences a potential systemic allergic/hypersensitivity reaction during the study as judged by the investigator. These samples may be tested for ADAs, ixekizumab serum concentration, and/or other laboratory tests needed to elucidate the cause of the allergic/hypersensitivity reaction.

8.4.7. Quick Inventory of Depressive Symptomatology—Self-Report (16 Items)

QIDS-SR16 is a self-administered, 16-item instrument intended to assess the existence and severity of symptoms of depression as listed in the American Psychiatric Association's Diagnostic and Statistical Manual of Mental Disorders, 4th Edition (DSM-IV) (APA 1994). A patient is asked to consider each statement as it relates to the way they have felt for the past 7 days. There is a 4-point scale for each item ranging from 0 to 3. The 16 items corresponding to 9 depression domains are summed to give a single score ranging from 0 to 27, with higher scores denoting greater symptom severity. The domains assessed by the instrument include: (1) sad mood, (2) concentration, (3) self-criticism, (4) suicidal ideation, (5) interest, (6) energy/fatigue, (7) sleep disturbance (initial, middle, and late insomnia or hypersomnia), (8) decrease/increase in appetite/weight, and (9) psychomotor agitation/retardation. Additional information and the QIDS-SR16 questions may be found at the University of Pittsburgh IDS/QIDS internet page [WWW]. A QIDS-SR16 assessment will be taken at times indicated in the Schedule of Activities (Appendix 2).

8.4.8. Columbia—Suicide Severity Rating Scale

The C-SSRS (Posner et al. 2007; Columbia University Medical Center [WWW]) is a scale that captures the occurrence, severity, and frequency of suicide-related ideations and behaviors during the assessment period. The C-SSRS must be administered by appropriately trained site personnel. The tool was developed by the National Institute of Mental Health Treatment of Adolescent Suicide Attempters trial group for the purpose of being a counterpart to the Columbia Classification Algorithm of Suicide Assessment (C-CASA) categorization of suicidal events. Patients will be assessed according to the Schedule of Activities (Appendix 2).

The Self-Harm Supplement Form is a one-question form that asks for the number of suicidal or nonsuicidal self-injurious behaviors the patient has experienced since the last assessment. For each unique event identified, a questionnaire (Self-Harm Follow-Up Form) which collects supplemental information on the self-injurious behavior is to be completed. This information is then documented in the eCRF. The Self-Harm Supplement Form will be completed according to the Schedule of Activities (Appendix 2).

8.4.9. Safety Monitoring

Lilly will periodically review evolving aggregate safety data within the study by appropriate methods.

If a study patient/subject experiences elevated ALT $\geq 3X$ ULN, ALP $\geq 2X$ ULN, or elevated TBL $\geq 2X$ ULN, clinical and laboratory monitoring should be initiated by the investigator. Details for hepatic monitoring depend upon the severity and persistence of observed laboratory test abnormalities. To ensure patient/subject safety and comply with regulatory guidance, the investigator is to consult with the Lilly CRP regarding collection of specific recommended clinical information and follow-up laboratory tests. See [Appendix 4](#).

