[44] At screening, have a lymphocyte count < 800 cells/ μL ($< 0.80 \times 10^3/\mu\text{L}$ or < 0.80 GI/L)

[45] At screening, have a platelet count $< 100,000$ cells/ μL ($< 100 \times 10^3/\mu\text{L}$ or < 100 GI/L)

[46] At screening, have aspartate aminotransferase (AST) or alanine aminotransferase (ALT) > 2.5 times the upper limit of normal (ULN)

(Note: The AST and ALT may be repeated once within a week if the initial response exceeds this limit, and the repeat value may be accepted if it meets this criterion.)

- [47] At screening, have a total white blood cell (WBC) count <3000 cells/ μ L (<3.00x10³/ μ L or <3.00 GI/L)
- [48] At screening, have hemoglobin <8.5 g/dL (85.0 g/L) for male patients and <8.0 g/dL (80 g/L) for female patients
- [49] Have other clinical laboratory test results at screening that are outside the normal reference range for the population and are considered clinically significant, per investigator assessment

Other Exclusions

- [50] Have donated more than 1 unit (approximately 450 mL) of blood within the last 4 weeks prior to screening (Visit 1) or intend to donate blood during the course of the study. These patients may be rescreened (1 time) to allow the required 4-week minimum time since donation of more than 1 unit of blood.
- [51] Are women who are lactating or breast feeding
- [52] Have any other condition that precludes the patient from following and completing the protocol, in the opinion of the investigator
- [53] Are investigator site personnel directly affiliated with this study and/or their immediate families. Immediate family is defined as a spouse, parent, child, or sibling, whether biological or legally adopted.
- [54] Are Lilly employees or its designee or are employees of third-party organizations (TPOs) involved in the study
- [55] Are unwilling or unable to comply with the use of a data collection device to directly record data from the subject

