7.1. Discontinuation from Study Treatment

The reason for and date of discontinuation from study treatment (investigational product) and reason for and date of discontinuation from study participation will be collected for all randomized patients.

For any patient discontinuing from study treatment, the investigational product will be withheld, and the patient will complete the ETV and the Post-Treatment Follow-Up Period (Period 4), as shown in the Schedule of Activities ([Appendix 2](#)).

Missing data may compromise the integrity of the study. Complete information from each patient is critical to achieving the fullest understanding of the potential benefits and risks of ixekizumab. All efforts should be made to keep patients in the study, to attend scheduled visits and procedures, and to take investigational product as medically appropriate.

Patients who meet any of the criteria described in Section 7.1.1 will be discontinued from the study treatment.

7.1.1. *Permanent Discontinuation from Study Treatment*

Patients may be permanently discontinued from study treatment in the following situations:

- [1] Discontinuation of the investigational product for abnormal liver tests should be considered by the investigator when a patient meets 1 of the following conditions after consultation with the Lilly designated medical monitor:
- ALT or AST >8X ULN
 - ALT or AST >5X ULN for more than 2 weeks
 - ALT or AST >3X ULN and total bilirubin level (TBL) >2X ULN or prothrombin time >1.5X ULN
 - ALT or AST >3X ULN with the appearance of fatigue, nausea, vomiting, right upper-quadrant pain or tenderness, fever, rash, and/or eosinophilia (>5% of total leukocytes)
 - ALP >2.5X ULN and TBL >2X ULN
 - ALP >2.5 ULN with the appearance of fatigue, nausea, vomiting, right quadrant pain or tenderness, fever, rash, and/or eosinophilia (>5%)

In addition, patients will be discontinued from the investigational product in the following circumstances:

- [2] Other laboratory tests (**Note:** Laboratory test(s) that may result in discontinuation based on a single result may be repeated only once if there is a technical error or clinical reason to believe a result may need to be retested. Laboratory tests can only be repeated after consultation with Lilly medical. Investigational product should not be administered in these cases until the retest result is available.):
- Neutrophil (segmented) counts (see safety monitoring for neutropenia in Section 8.4.9.1);

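### The hepatic monitoring trigger in Protocol 8.4.9 omits AST, so an isolated AST rise can meet 3 of the 4 transaminase criteria for considering discontinuation with no monitoring trigger met

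*Protocol*

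**What the plan says.** **Trigger.** Protocol 8.4.9 (Safety Monitoring) sets the point at which hepatic follow-up begins: "If a study patient/subject experiences elevated ALT $\geq 3X$ ULN, ALP $\geq 2X$ ULN, or elevated TBL $\geq 2X$ ULN, clinical and laboratory monitoring" is then for the investigator to start. It adds that "the investigator is to consult with the Lilly CRP regarding collection of specific recommended clinical information and follow-up laboratory tests", and points to Appendix 4 for the tests. The triggers are ALT, ALP and total bilirubin (TBL).

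**Discontinuation.** Protocol 7.1.1 [1] says that stopping because of liver-test abnormalities "should be considered by the investigator when a patient meets 1 of the following conditions after consultation with the Lilly designated medical monitor". It has four transaminase criteria, and each names both enzymes:
- "ALT or AST >8X ULN";
- "ALT or AST >5X ULN for more than 2 weeks";
- either enzyme above 3X ULN together with TBL above 2X ULN or prothrombin time above 1.5X ULN;
- "ALT or AST >3X ULN with the appearance of fatigue, nausea, vomiting", other listed symptoms, or eosinophilia.

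Two further criteria use ALP above 2.5X ULN, one with TBL above 2X ULN and one with symptoms or eosinophilia.

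**AST elsewhere.** Exclusion [46] in Protocol 5.2 covers patients who at screening "have aspartate aminotransferase (AST) or alanine aminotransferase (ALT") above 2.5 times ULN. The adverse events of special interest in Protocol 8.2.2 include "liver function test changes/enzyme elevations (ALT, AST, bilirubin, and alkaline phosphatase"). Protocol 8.4.5 holds both enzymes to no more than 2 times ULN before randomization in patients rescreened on latent-TB therapy. SAP Table RHBQ.6.6 lists patients with either enzyme at or above 3X ULN.

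**The concern.** Of the five protocol provisions that set a rule on transaminases or list them (leaving aside the test lists in Appendices 3 and 4), 8.4.9 is the only one without AST. On treatment, an ALT of 3X ULN starts monitoring and a call to the sponsor's physician. An AST of 6X ULN with the other tests below their triggers starts neither.

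Three features of the plan make the missing step matter:
- The criterion of more than 5X ULN for more than 2 weeks cannot be judged from one value. Scheduled chemistry can be up to 12 weeks apart.
- Prothrombin time is among the Appendix 4 hepatic tests but not in the routine Appendix 3 panel. That branch of the third criterion is unlikely to be assessed unless hepatic follow-up has begun.
- Patients rescreened after at least 4 weeks of latent-TB therapy are checked for hepatotoxicity on both enzymes before randomization, and must complete that therapy during the study. Once they are on study, 8.4.9 gives no AST level at which to act.

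**Working it through.** The plan states no figure to reproduce. The check is whether each discontinuation criterion can be met while every 8.4.9 trigger is unmet.

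**Inputs (multiples of ULN).** Triggers from 8.4.9: ALT ≥3, ALP ≥2, TBL ≥2. Criteria from 7.1.1 [1]: the six described above.

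**ALT route.** Each of the four transaminase criteria requires at least ALT >3, which implies ALT ≥3. Untriggered: 0 of 4. For the two criteria that start at >3X, the trigger and the criterion share essentially the same cut-off. For the other two, the trigger comes earlier.

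**ALP route.** Both criteria require ALP >2.5, which implies ALP ≥2. Untriggered: 0 of 2.

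**AST route.** Hold ALT <3, ALP <2 and TBL <2, so that no trigger is met:

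| Criterion reached through AST | Can it be met with no trigger? |
|---|---|
| AST >8 | Yes |
| AST >5 for more than 2 weeks | Yes |
| AST >3 and TBL >2 | No: TBL >2 implies TBL ≥2 |
| AST >3 and prothrombin time >1.5 | Yes |
| AST >3 with symptoms or eosinophilia | Yes |

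The third and fourth rows are the two branches of one criterion. The count is therefore 3 of 4 in full, plus one branch of the remaining criterion. Enumerating combinations of the enzyme values, prothrombin time, duration and symptoms gave the same result.

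**With AST ≥3 added to the trigger.** All four criteria require AST >3, which implies AST ≥3. Untriggered: 0 of 4. The enumeration again agreed.

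**Time to the next scheduled value.** In the Schedule of Activities (Appendix 2), serum chemistry from baseline falls at Weeks 0, 4, 12, 16, 28, 40 and 52. The gaps are 4, 8, 4, 12, 12 and 12 weeks. An AST of 6X ULN first seen at Week 16, for example, would next be measured on schedule at Week 28.

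**The case against.** The strongest reply is that 3 of 4 counts logical routes, not patients left unsupervised. Two of the three criteria (AST >8X, and AST >3X with symptoms or eosinophilia) can be recognised at a single observation, and 7.1.1 [1] then calls for consultation with the medical monitor. That is right. It narrows the practical gap to an asymptomatic AST from 3X to 8X ULN, plus the duration criterion and the prothrombin-time branch, both of which need further testing.

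It can also be said that only 7.1.1 [1] and 8.4.9 set numerical transaminase thresholds on treatment, so the five-provision comparison proves less than it seems. The latent-TB check, likewise, is an eligibility condition and not a monitoring trigger. Both points are fair. The mismatch between 8.4.9 and 7.1.1 [1] is enough without them.

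The SAP's combined hepatic criterion and its eDISH plot use ALT with bilirubin, which would fit a deliberate ALT-based convention. The documents do not state one, however, and such a convention would not explain why AST ranks equally with ALT in 7.1.1 [1].

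Finally, other provisions reach such a patient. Protocol 8.2 requires documented review of every laboratory report and follow-up of medically important events. Criterion [4] in 7.1.1 requires the sponsor to be told at once of a laboratory change that the investigator thinks merits stopping. Appendix 3 allows unscheduled chemistry, and Appendix 4 tests may be used for any treatment-emergent hepatic abnormality. All of these depend on the investigator's judgement or act late, and the SAP listing is a reporting output. Section 8.4.9 is itself loosely worded, with no fixed interval or test even for ALT, but it does name a level at which something must start. For AST no provision does so before a discontinuation criterion is met.

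**Conclusion.** The concern holds. Read as written, 8.4.9 lets an isolated AST rise meet three of the four transaminase criteria in 7.1.1 [1], and the prothrombin-time branch of the fourth, with no monitoring trigger met. The corresponding counts are 0 of 4 for ALT and 0 of 2 for ALP. The practical loss is the early step: protocol-directed monitoring and sponsor consultation for an AST rise that has not yet reached a discontinuation criterion.

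The size in patients is unknown. The documents give no frequency for isolated AST elevation, it may be small among about 146 patients, and some rises will not be hepatic. The 7.1.1 [1] criteria only ask the investigator to consider stopping. No efficacy analysis is affected, and no AST data are lost, since the SAP summarises AST elevations. The change should be made because it corrects a stated safety rule at little cost.

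**What to change.** In Protocol 8.4.9, make the first trigger ALT or AST at or above 3X ULN. That is the level already used there for ALT, and in the SAP hepatic listing for both enzymes. AST is already in the Appendix 3 chemistry panel, so no new scheduled sampling is needed. The cost is a short clarification or amendment and a few additional triggered evaluations, some for AST rises that turn out not to be hepatic. The change puts AST through the same process as ALT. It does not set a repeat interval or require a prothrombin time for either enzyme.

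Optional and minor: add AST to the SAP's combined hepatic criterion so that it matches the listing, subject to the program safety analysis plan, which takes precedence over the SAP on special safety topics.
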